14.6. Secondary Analysis

CLUE Vision Score:

Overall quality of vision scores will be analyzed using a linear mixed model adjusting for baseline values as fixed covariates. The model will include the experimental design factors: sequence of lens wear, period, lens type as fixed effects. The covariance between residual errors from the same subject across lens wearing periods will be selected based on the finite-sample corrected Akaike's Information Criterion (Keselman et al. 1998). Covariance structures considered may include: Homogenous compound symmetry (CS) and Unstructured covariance structure (UN). The structure that returns the lowest Akaike Information Criteria Corrected (AICC) will be selected as the structure that best fit the data.

Comparisons will be carried out using 95% confidence intervals constructed of least squared means (LSM) from the linear mixed models. Statistical superiority will be concluded if the lower limit of the confidence intervals of the test lens is above 32 points.

In all models, the Kenward and Roger method (Kenward and Roger, 1997) will be used for the calculation of the denominator of degrees of freedom.

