2.3. Hypotheses

Primary Hypotheses

1. After 8-12 days of lens wear, the distance, binocular, high luminance, high contrast visual performance of the two test lenses will be superior to +0.01 logMAR.
2. After 8-12 days of lens wear, the near, binocular, high luminance, high contrast visual performance of the two test lenses will be superior to +0.17 logMAR.

Secondary Hypothesis

1. After 8-12 days of lens wear, the overall quality of vision of the two test lenses will be superior to 32 CLUE points.

Other Hypotheses: Not applicable.

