14.4. Level of Statistical Significance

All planned analysis for this study will be conducted with an overall type I error rate of 5%. No adjustment for multiple comparisons will be conducted unless specified otherwise. This is a pilot study and all the hypotheses are exploratory in nature.

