14.5. Primary Analysis

Primary efficacy analysis:

Visual Performance:

Near and distance binocular, high luminance, high contrast visual performance on logMAR scale will be analyzed separately using a linear mixed model to test for the difference between the study lens systems. Each model will include the experimental design factors: sequence of lens wear, lens wearing period and lens type as fixed effects. Other baseline characteristics known of importance such as age, gender, and/or add power will be included as fixed covariates when appropriate. The covariance between residual errors from the same subject across lens wearing periods will be selected based on the finite-sample corrected Akaike's Information Criterion (Keselman et al. 1998). Covariance structures considered may include: Homogenous compound symmetry (CS) and Unstructured covariance structure (UN). The structure that returns the lowest Akaike Information Criteria Corrected (AICC) will be selected as the structure that best fit the data.

Comparisons will be carried out using 95% confidence intervals constructed of least squared means (LSM) from the linear mixed models. Statistical superiority will be concluded if the upper limit of the confidence intervals of the test lens is below +0.01 logMAR for distance and +0.17 for near.

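### The CLUE rule in 14.6 tests baseline-adjusted lens means against a fixed 32 points, so its intervals are modestly too narrow for a population-mean claim

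*Combined protocol and SAP*

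**What the plan says.** The secondary hypothesis in 2.3 is that "the overall quality of vision of the two test lenses will be superior to 32 CLUE points". For the analysis, 14.6 specifies: "Overall quality of vision scores will be analyzed using a linear mixed model adjusting for baseline values as fixed covariates". Sequence, period and lens type are the other fixed effects. Then: "Comparisons will be carried out using 95% confidence intervals constructed of least squared means (LSM) from the linear mixed models". The decision rule is: "Statistical superiority will be concluded if the lower limit of the confidence intervals of the test lens is above 32 points". So baseline adjustment is mandatory for CLUE, and the decision compares each lens's own mean with a constant.

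Section 14.5 has the same structure for visual performance, where superiority requires that "the upper limit of the confidence intervals of the test lens is below +0.01 logMAR for distance and +0.17 for near". There, however, the covariates are optional: "Other baseline characteristics known of importance such as age, gender, and/or add power will be included as fixed covariates when appropriate".

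Section 14.4 states: "All planned analysis for this study will be conducted with an overall type I error rate of 5" per cent. It makes no multiplicity adjustment and calls all hypotheses exploratory. The plan does not give the covariate value at which a least-squares mean is evaluated. It does not say that inference is conditional on the enrolled baselines, and it adds no variance for the sampled baseline mean. The Kenward-Roger method is named only for denominator degrees of freedom.

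**The concern.** Baseline adjustment is right for a lens-versus-lens difference. The sampled baseline mean cancels, and the smaller residual variance is a real gain in precision.

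It does not cancel in an absolute lens mean set against a constant. With complete data and balanced sequences, the least-squares mean at the sample baseline mean is essentially the plain average for that lens. Adjustment hardly moves the estimate but shrinks its standard error. If the claim concerns the mean that presbyopic wearers would score with the lens, the chance that this sample had a favourable average baseline is real uncertainty, and the interval leaves it out.

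At stake is whether the threshold tests keep the error rate stated in 14.4. The better baseline predicts outcome, the further the rate drifts.

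**Working it through.** **Inputs from the documents.** Two-sided 95% interval, one limit used (14.6); CLUE cut-off 32 (14.6); CLUE SD 20 and general-wearer average 60 (2.2); 60 completers (14.2); 2×2 crossover (5.1), so each lens mean uses all completers.

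**Assumed.** The baseline–outcome correlation rho (R² = rho²), shown as a range. In the crossover simulation only, a correlation of 0.6 between the two lenses' scores and 0.7 between the two baselines.

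**The plan's own figure.** A two-sided 95% interval gives 5.0% non-coverage, hence 2.5% for the single limit used. A simulated crossover at n = 60 with no covariate gave 5.0% and 2.7% (6,000 runs), so the stated level is reproduced.

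**Formula.** For one lens with score variance σ²:

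- variance reported by the adjusted model at the sample baseline mean: σ²(1−R²)/n
- variance of the same estimate around the population mean: σ²/n
- omitted term: β²·Var(X̄) = σ²R²/n

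The width ratio is sqrt(1−R²), and the one-sided error with the true mean at the cut-off is 1 − Φ(1.96·sqrt(1−R²)).

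| R² (assumed) | sqrt(1−R²) | 1.96·sqrt(1−R²) | One-sided error, formula | One-sample simulation, n = 60, 20,000 runs |
|---|---|---|---|---|
| 0.10 | 0.949 | 1.859 | 3.1% | 3.1% |
| 0.20 | 0.894 | 1.753 | 4.0% | 4.1% |
| 0.30 | 0.837 | 1.640 | 5.1% | 4.8% |
| 0.50 | 0.707 | 1.386 | 8.3% | 8.2% |

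Without the covariate the same simulation gave 2.4–2.6%.

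**Doubling point.** An error of 5.0% needs 1.96·sqrt(1−R²) = 1.645, so R² = 1 − (1.645/1.960)² = 0.296, or rho of about 0.54.

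**Crossover check.** The simulation used REML with compound symmetry, and a t reference with n − 3 degrees of freedom standing in for Kenward-Roger. Section 7.2 collects a baseline questionnaire at Visits 1 and 4, so both choices of baseline were run.

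| rho | Formula | Visit 1 baseline (6,000 runs) | Period-specific baseline (3,000 runs) |
|---|---|---|---|
| 0.30 | 3.1% | 2.7% | 2.9% |
| 0.50 | 4.5% | 4.4% | 4.9% |
| 0.55 | 5.1% | 5.3% | 5.5% |
| 0.70 | 8.1% | 7.6% | 8.0% |

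**Size in CLUE points.** The half-width for a population mean is 1.96 × 20/√60 = 5.06. At R² = 0.30 the adjusted model reports 5.06 × 0.837 = 4.23, which is 0.83 short. The verdict changes only if the observed mean lies between 32 + 4.23 = 36.23 and 32 + 5.06 = 37.06.

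**The case against.** The strongest reply is that an adjusted least-squares mean has a valid interval conditional on the enrolled baselines, and that 2.3 names no superpopulation. Subjects come from the site's database (3.4) under refractive and ADD recruitment targets, so the sampling variance of a population baseline mean is not clear-cut. This carries some weight, but it does not rescue the rule. The hypotheses in 2.3 are about the lenses, 14.2 says the data will be used to design future trials, and the plan nowhere declares a conditional target. No recruitment target fixes the CLUE baseline.

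Second, the covariate could be set at a fixed reference value. Simulated error then returned to 2.7% at rho 0.55 and 2.3% at rho 0.70. That was with the reference equal to the true population baseline mean, which for this presbyopic group is unknown. The plan names no such value.

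Third, no baseline–outcome correlation is given, and baseline is scored with habitual lenses, which are different products. A high R² cannot be presumed. This stands.

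Fourth, if 2.3 requires both lenses to pass, joint error with both true means at 32 was only 1.4–1.8% at rho 0.55. This also stands for that reading. Without the covariate the joint figure was 0.6%, and it moves towards the single-lens rate if one lens is clearly above 32.

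Fifth, this is an unpowered, exploratory pilot with no multiplicity adjustment. That limits the consequence. But 14.4 still states a level and 14.6 still concludes superiority.

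**Conclusion.** The point holds for CLUE, where adjustment is mandatory. It assumes that the least-squares mean is evaluated at the sample baseline mean and that the claim concerns a population mean. One-sided error per lens is then about 3.1%, 5% and 8% at assumed R² of 0.10, 0.30 and 0.50, against 2.5%. These rates apply when the true mean is exactly 32, far below the general-wearer average of 60 in 2.2, although this group may differ. With a half-width shortfall of about 0.8 points at R² = 0.30, the practical effect is modest.

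Three stronger readings are not supported:

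- **That the false-superiority rate doubles as a matter of course.** Doubling needs baseline to explain about 30% of the variance, and the documents give no such figure. At rho 0.3 or less the formula gives at most 1.23 times nominal.
- **That the logMAR cut-offs are equally affected.** In 14.5 covariates enter only at discretion, and ADD is partly balanced by the recruitment target of 30 subjects per group in the synopsis. The effect arises there only if predictive covariates such as age are included, and is likely smaller.
- **That gender weighting materially shifts the logMAR means.** The plan does not commit to including gender and gives neither a gender split nor a gender effect. Equal weighting would also be a legitimate target.

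**What to change.** In 14.6, take the decision against 32 points from a model with sequence, period and lens only. Keep the baseline-adjusted model for the lens-versus-lens difference, where it gains precision legitimately. Add the same sentence to 14.5 for the +0.01 and +0.17 logMAR rules, to apply if covariates are used there. Without the covariate, simulated one-sided error was 2.7%, the nominal level within simulation error.

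Alternatively, keep the covariate and add β²·Var(X̄) to the variance of each least-squares mean before forming the threshold interval.

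The cost is a sentence in each of two sections and one extra model run. Threshold intervals become slightly wider, for example 5.06 instead of 4.23 points at SD 20, n = 60 and R² = 0.30. Each endpoint would then have two models, so the plan should say which one supports which statement.

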14.7. Other Exploratory Analyses

Not applicable.

14.8. Interim Analysis

Not Applicable

14.9. Procedure for Handling Missing Data and Drop-Outs

Missing or spurious values will not be imputed. The count of missing values will be included in the summary tables and listings.

Subject dropout is expected to be one of the main reasons of missing data in this clinical trial. Past clinical trials don't provide the evidence that subject dropout is systematic or not-at-random. To evaluate the impact of missing data, sensitivity analysis will be conducted using multiple imputation methods if the proportion of subject dropout is greater than the 15%. The SAS/STAT procedures PROC MI and PROC MIANALYZE will be utilized with a parametric regression method used to make at least 5 imputations.

14.10. Procedure for Reporting Deviations from Statistical Plan

The analysis will be conducted according to that specified in above sections. There are no known reasons for which it is planned to deviate from these analysis methods. If for any reason a change is made, the change will be documented in the study report along with a justification for the change.

15. DATA HANDLING AND RECORD KEEPING/ARCHIVING

15.1. Electronic Case Report Form/Data Collection

The data for this study will be captured on electronic case report forms (eCRFs) using an Bioclinica Express version 5.5 EDC system. An authorized data originator will enter study data into the eCRFs using the EDC system. Data collected on equipment that is not captured in EDC will be formatted to the specification of the JJVC database manager and sent to JJVC for analysis.

External Date Sources for this study include: Not Applicable

The clinical data will be recorded on dedicated eCRFs specifically designed to match the study procedures for each visit. Once completed, the eCRFs will be reviewed for accuracy and completeness and signed by the Investigator. The sponsor or sponsor's representatives will be authorized to gain access to the subject recordation for the purposes of monitoring and auditing the study.

Edit checks, electronic queries, and audit trails are built into the system to ensure accurate and complete data collection. Data will be transmitted from the clinical site to a secure central database as forms are completed or updated, ensuring information accuracy, security, and confidentiality. After the final database lock, the Investigator will be provided with Individual Patient Profiles (IPP) including the full audit trail on electronic media in PDF format for all the study data. The IPP must be retained in the study files as a certified copy of the source data for the study.

The content and structure of the eCRFs are compliant with ISO14155:2011.

15.2. Subject Record

At a minimum, subject record should be available for the following:

- subject identification
- eligibility
- study identification
- study discussion
- provision of and date of informed consent
- visit dates
- results of safety and efficacy parameters as required by the protocol
- a record of all adverse events
- follow-up of adverse events
- medical history and concomitant medication
- test article receipt/dispensing/return records
- date of study completion
- reason for early discontinuation of test article or withdrawal from the study, if applicable

The subject record is the eCRF or an external record. The author of an entry in the subject record must be identifiable. The first point of entry is the source record.

Adverse event notes must be reviewed and initialed by the Investigator.

16. DATA MANAGEMENT

16.1. Access to Source Data/Document

The Investigator/Institution will permit trial-related monitoring, audits, IEC/IRB review and regulatory inspection(s) by providing direct access to source data/documents. Should the clinical site be contacted for an audit by an IEC/IRB or regulatory authority, JJVC must be contacted and notified in writing within 24 hours.

16.2. Confidentiality of Information

Information concerning the investigational product and patent application processes, scientific data or other pertinent information is confidential and remains the property of JJVC. The Investigator may use this information for the purposes of the study only. It is understood by the Investigator that JJVC will use information developed in this clinical study about the development of the investigational product and therefore may disclose it as required to other clinical investigators and to regulatory agencies. In order to allow the use of the information derived from this clinical study, the Investigator understands that he/she has an obligation to provide complete test results and all data developed during this study to the Sponsor.

16.3. Data Quality Assurance

Steps will be taken to ensure the accuracy and reliability of data, include the selection of qualified investigators and appropriate clinical sites and review of protocol procedures with the Principal Investigator. The Principal Investigator, in turn, must ensure that all Sub-Investigators and clinical site personnel are familiar with the protocol and all study-specific procedures and have appropriate knowledge of the study article.

Training on case report form completion will be provided to clinical site personnel before the start of the study. The Sponsor will review case report forms for accuracy and completeness remotely during the conduct of the study, during monitoring visits, and after transmission to data management. Any data discrepancies will be resolved with the Investigator or designee, as appropriate.

Quality Assurance representatives from JJVC may visit clinical sites to review data produced during the study and to access compliance with applicable regulations pertaining to the conduct of clinical trials. The clinical sites will provide direct access to study-related source data/documents and reports for monitoring and auditing by JJVC and for inspection by local and regulatory authorities.

17. MONITORING

The study monitors will maintain close contact with the Principal Investigator and the Investigator's designated clinical site personnel. The monitor's responsibilities will include:

- Ensuring that the investigation is being conducted according to the protocol, any subsequent amendments, and regulatory requirements are maintained
- Ensuring the rights and wellbeing of subjects are protected
- Ensuring adequate resources, including facilities, laboratories, equipment, and qualified clinical site personnel
- Ensuring that protocol deviations are documented with corrective action plans, as applicable
- Ensuring that the clinical site has sufficient test article and supplies
- Clarifying questions regarding the study
- Resolving study issues or problems that may arise
- Reviewing of study records and source documentation verification in accordance with the monitoring plan

18. ETHICAL AND REGULATORY ASPECTS

18.1. Study-Specific Design Considerations

Potential subjects will be fully informed of the risks and requirements of the study and, during the study, subjects will be given any new information that may affect their decision to continue participation. Subjects will be told that their consent to participate in the study is voluntary and may be withdrawn at any time with no reason given and without penalty or loss of benefits to which they would otherwise be entitled. Only subjects who are fully able to understand the risks, benefits, and potential adverse events of the study, and provide their consent voluntarily will be enrolled.

18.2. Investigator Responsibility

The Principal Investigator is responsible for ensuring that the clinical study is performed in accordance with the signed agreement, the investigational plan, Section 4 of the ICH E6 guidelines on Good Clinical Practice (GCP), and applicable regulatory requirements. GCP is an international ethical and scientific quality standard for designing, conducting, recording, and reporting studies that involve the participation of human subjects. Compliance with this standard provides public assurance that the rights, safety, and well-being of study subjects are protected, consistent with the principles of the Declaration of Helsinki 64th WMA General Assembly 2013 and that the clinical study data are credible. The Investigator must maintain clinical study files in accordance with Section 8 of the ICH E6 guidelines on Good Clinical Practice (GCP), and applicable regulatory requirements.

18.3. Independent Ethics Committee or Institutional Review Board (IEC/IRB)

Before the start of the study, the Investigator (or Sponsor when applicable) will provide the IEC/IRB with current and complete copies of the following documents (where applicable):

- Final protocol and, if applicable, amendments
- Sponsor-approved informed consent form (and any other written materials to be provided to the subjects)
- Investigator's Brochure (or equivalent information) and amendments
- Sponsor-approved subject recruitment materials
- Information on compensation for study-related injuries or payment to subjects for participation in the study
- Investigator's curriculum vitae, clinical licenses, or equivalent information (unless not required, as documented by IEC/IRB)
- Information regarding funding, name of the Sponsor, institutional affiliations, other potential conflicts of interest, and incentives for subjects
- Any other documents that the IEC/IRB requests to fulfill its obligation

This study will be undertaken only after IEC/IRB has given full approval of the final protocol, amendments (if any), the informed consent form, applicable recruiting materials, and subject compensation programs, and the Sponsor has received a copy of this approval. This approval letter must be dated and must clearly identify the documents being approved.

During the study the Investigator (or Sponsor when applicable) will send the following documents to the IEC/IRB for their review and approval, where appropriate:

- Protocol amendments
- Revision(s) to informed consent form and any other written materials to be provided to subjects
- If applicable, new or revised subject recruitment materials approved by the Sponsor
- Revisions to compensation for study-related injuries or payment to subjects for participation in the study
- Investigator's Brochure amendments or new edition(s)
- Summaries of the status of the study (at least annually or at intervals stipulated in guidelines of the IEC/IRB)
- Reports of adverse events that are serious, unanticipated, and associated with the test articles, according to the IRB's requirements
- New information that may adversely affect the safety of the subjects or the conduct of the study
- Major protocol deviations as required by the IEC/IRB
- Report of deaths of subjects under the Investigator's care
- Notification if a new Investigator is responsible for the study at the clinical site
- Any other requirements of the IEC/IRB

For protocol amendments that increase subject risk, the amendment and applicable informed consent form revisions must be submitted promptly to the IEC/IRB for review and approval before implementation of the change(s).

At least once a year, the IEC/IRB will review and reapprove this clinical study. This request should be documented in writing.

At the end of the study, the Investigator (or Sponsor where required) will notify the IEC/IRB about the study completion. Documentation of this notification must be retained at the clinical site and a copy provided to the CRO or Sponsor as applicable.

18.4. Informed Consent

Each subject must give written consent according to local requirements after the nature of the study has been fully explained. The consent form must be signed before performance of any study-related activity. The consent form that is used must be approved by both the Sponsor and by the reviewing IEC/IRB. The informed consent is in accordance with principles that originated in the Declaration of Helsinki, current ICH and GCP guidelines, applicable regulatory requirements, and Sponsor policy.

Before entry into the study, the Investigator or an authorized member of the clinical site personnel must explain to potential subject the aims, methods, reasonably anticipated benefits, and potential hazards of the study, and any discomfort it may entail. Subjects will be informed that their participation is voluntary and that they may withdraw consent to participate at any time.

The subject will be given sufficient time to read the informed consent form and the opportunity to ask questions. After this explanation and before entry into the study, consent should be appropriately recorded by means of the subject's dated signature. After having obtained the consent, a copy of the informed consent form must be given to the subject.

